2.2 Secondary Objective

[figure not shown]
The secondary objective is to compare adverse outcomes, length of stay, days to return to school or work, costs of care and quality of life measures between those that receive laser hair depilation and those that receive mechanical/chemical hair depilation and hygiene recommendations.

3. Investigational Plan

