3.1 Study Design

This is a prospective, randomized single-site trial measuring the safety and feasibility of treating children (12-20 years old) with pilonidal disease using laser hair depilation. There will be two cohorts; those who receive laser hair depilation treatments and those that receive only chemical/mechanical depilation. There will be two phases: Phase One – Pilot study to measure safety and tolerance and Phase Two – Randomized control trial to determine efficacy as a treatment of pilonidal disease and as a possible treatment to intervene on future recurrence.

Enrollment:

[figure not shown]

Randomization:

Randomization

Chemical depilation (cream application as directed) or Mechanical depilation (via shaving)

Treatment:

Follow-up:

Surgical clinic or telephone follow up once monthly for one year to assess for tolerance (traditional pain scale 1-10), resolution, recurrence of cellulitis or abscess, or development of chronic sinus requiring surgical excision

8

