Laser Depilation: The two lasers that will be used in this study (810 nm or Nd:YAG) are both FDA approved for hair removal in all areas of the human body including the back. These lasers are being used for hair removal in the back region for which they have FDA approval; however

they do not have specific approval for pilonidal disease. In discussion with [name], Director of the Drug and Device Development Services at the RINCH, we believe that an IDE is not necessary for this study as we are using an approved device for investigational purposes with non-significant risk. Laser use in this study poses minimal risk to the patient and these minimal risks are similar to the risks associated with hair removal in the back and other regions of the body for which devices are already FDA approved.

Follow-Up:

Initial follow up for the laser depilation group will be performed to assess for tolerance of the laser treatment. This will occur via use of a REDCap database system where patients can report their pain every 6 hours (with the exception of the overnight period from 8pm-8am) for the first 48 hours after their laser hair depilation treatment. Text message reminders will be sent to these patients for them to give us their pain scores. For those with smart phones, we can text them the link to their REDCap survey, and for those without smart phones or without consistent access to the internet, we can receive their pain scores via return text messages from them. Once tolerance is established, patients will return to surgical clinic every month for their laser or placebo visit. After the 5th clinic visit, they will receive a telephone call monthly to assess for any evidence of resolution or recurrence of disease up to 1 year after the completion of the treatments.

5. Statistical Considerations

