5.3. Sample Size and Power

We anticipate a group of 10 patients to measure laser depilation tolerance. If tolerance is good (>95% the phase 1 patients pain scores < 4 with no deep second degree burns), we will proceed to the phase 2 study. The sample size for phase 2 will be 164 patients. Since the predicted recurrence rate in the control group based on previous studies may be 20% and in the laser group

will be 5%, we would need 82 patients in each treatment group in order to detect this difference at a one-sided alpha of 0.025 using a Fisher exact test.

6. Study Administration

Phase One: Pilot Study

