7.2.4. Data safety and monitoring

Tolerance to the laser treatments will be monitored closely, especially in the first 48 hours of the laser hair depilation treatments. Treatments will stop at any point in which the patient reports enough discomfort to terminate therapy. Areas treated will be observed for cutaneous changes including excessive erythema, discoloration, or tenderness. Data will be monitored by research team members daily. They will ensure that all data (clinical data and questionnaires) collected are correctly completed. Any suggestion of an adverse event identified by this person will be discussed with the principal investigator immediately.

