7.4. Informed Consent/Assent

All informed consents and assents will be performed by a physician-member of the research team.

If the child and legal guardian (for subjects < 18 years) are interested in participating in this study, a physician-member of the research team will guide the child and legal guardian through the informed consent/assent process. Written informed consent will be obtained from one legal guardian of subjects < 18 years of age and from the patient him or herself if he or she is ≥ 18 years of age. Written informed assent will be obtained from subjects ≥ 9 and < 18 years of age.

Refusal to participate in the study will not affect the child's clinical care. Participants and their legal guardian have the right to switch to the standard treatment and/or withdraw from the study at any time. Withdrawal from the study will not affect receipt of clinical care.

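### Section 4 gives no recurrence follow-up schedule for patients who stop treatment early, it conflicts with 3.1 and 3.2.1, and no section keeps these patients in their randomised arm

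*Combined protocol and SAP*

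**What the plan says.** **Stopping and switching.** Section 7.2.4: "Treatments will stop at any point in which the patient reports enough discomfort to terminate therapy". Section 7.4: "Participants and their legal guardian have the right to switch to the standard treatment and/or withdraw from the study at any time". Section 7.2.5 counts inability to tolerate the laser among the adverse events to be tracked. In section 4, control patients get a simulated treatment in which the laser is not fired.

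**Follow-up.** Section 4, Follow-Up, has patients return monthly once tolerance is established. It then says: "After the 5th clinic visit, they will receive a telephone call monthly to assess for any evidence of resolution or recurrence of disease". These calls run until one year after treatment is completed. Section 3.1 has clinic or telephone follow-up monthly for a year. Section 3.2.1 has it monthly for a year counted from the initial treatment. Neither makes it depend on a fifth visit.

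**Groups.** Section 3.1: "There will be two cohorts; those who receive laser hair depilation treatments and those that receive only chemical/mechanical depilation". Section 2.2 frames the secondary comparison as "between those that receive laser hair depilation and those that receive mechanical/chemical hair depilation and hygiene recommendations". Section 4 speaks of patients randomised to laser or placebo.

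**Analysis.** Section 5.2 compares the one-year recurrence proportion between the treatment groups with a Fisher exact test. It names no analysis population, no rule for stoppers or switchers and no rule for missing one-year outcomes.

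**The concern.** The primary endpoint of Phase Two is recurrence at one year, so every randomised patient's status at one year is needed. The section that describes the contacts in most detail is written for patients who complete five visits. Staff who work from it have no instruction to keep calling someone who stopped after the second session. Because stopping for discomfort should be concentrated in the laser arm, the missing outcomes would be too.

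Loss in one arm for a treatment-related reason means that the remaining laser patients are no longer a randomised comparator for the controls. If those who stop have a higher recurrence risk, losing them makes the laser look better than it is. Outcomes that were never collected cannot be recovered later. With no stated analysis population, the handling of these patients could also be settled after the data are seen.

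**Working it through.** **1. The plan's own figure.** Section 5.3 assumes 20% recurrence in control. For the laser group it says: "will be 5%, we would need 82 patients in each treatment group in order to detect this difference". The test is at a "one-sided alpha of 0.025 using a Fisher exact test". No power is stated. Exact binomial enumeration, rejecting when the hypergeometric tail is at most 0.025, gives 79.9% power at 81 per arm and 80.5% at 82. So 82 reproduces if 80% power was intended. The total of 164 = 2 × 82 leaves no reserve for loss. At 10% loss from both arms (82 × 0.9 ≈ 74 per arm) power is 75.2%.

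**2. The follow-up texts side by side.** Five treatments 4 to 6 weeks apart put the fifth at 4 × 4 = 16 to 4 × 6 = 24 weeks after the first.

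| Section | Origin | End | Depends on visit 5 or completion? |
|---|---|---|---|
| 3.1 | not stated | one year | no |
| 3.2.1 | initial treatment | week 52 | no |
| 4, Follow-Up | completion of treatments | 16 + 52 = week 68 to 24 + 52 = week 76 | yes |

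For a patient who stops after treatments 1 to 4, section 4 defines neither the start of the calls nor their end. Section 3.2.1 defines both. No section takes precedence over another.

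**3. What loss from the laser arm could do to the test.** The documents give neither a stopping rate nor a recurrence rate in stoppers, so both are assumed here. Assume no laser effect and 20% recurrence in each arm as randomised, so 0.20 × 82 = 16.4 expected recurrences per arm. Let *f* laser patients stop, recur at rate *r* and be lost. The remaining laser patients then recur at

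(16.4 − *r* × *f*) / (82 − *f*).

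For *f* = 8 and *r* = 0.40 this is (16.4 − 3.2) / 74 = 17.8%, against 20.0% in control. For *f* = 12 it is (16.4 − 4.8) / 70 = 16.6%. For *f* = 4 it is (16.4 − 1.6) / 78 = 19.0%. For *f* = 8 and *r* = 0.30 it is (16.4 − 2.4) / 74 = 18.9%.

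Exact rejection rates of the one-sided Fisher test in favour of laser:

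| Stoppers lost (of 82) | Recurrence in stoppers | All analysed as randomised | Stoppers lost |
|---|---|---|---|
| 4 | 40% | 1.5% | 2.4% |
| 8 | 40% | 1.5% | 3.4% |
| 12 | 40% | 1.4% | 4.9% |
| 8 | 30% | 1.5% | 2.3% |
| 8 | 20% | 1.5% | about 1.5% |

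The Fisher test is conservative here (1.5% actual size against 2.5% nominal), which absorbs the milder scenarios. The nominal level is exceeded only with 8 or 12 stoppers at twice the average risk.

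**The case against.** A reader might infer that the plan as a whole drops patients who stop. It does not. Sections 3.1 and 3.2.1 provide a year of monthly follow-up for everyone. The section 4 sentence can be read as marking the change from clinic visits to telephone for a patient who is on schedule. Section 7.2.4 stops treatment, not follow-up, and 7.4 names switching and withdrawing separately. Section 7.1 already collects the number and dates of treatments and later episodes of folliculitis or drainage. This stands, and it makes the point a conflict and a silence, not a rule that removes patients.

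A reader might also infer an as-treated analysis from the word receive in 2.2 and 3.1, with switchers counted as controls. The documents do not support that. The wording is descriptive, 2.2 concerns secondary objectives, and section 4 uses the language of randomisation. In 3.1 the second cohort received only chemical or mechanical depilation, so a patient with even one laser session does not fit it. No figure for reassignment to control is therefore given.

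Finally, the inflation rests on chosen inputs. Phase Two opens only if more than 95% of Phase One patients have pain scores below 4 with no deep second degree burns. Taken as a guide, 5% of 82 is about 4 stoppers, where the rate stays under 2.5%. Excluding actively inflamed sinuses at entry also weakens the case for a doubled risk. Both points have force. But with ten patients the criterion can be met only by 10 of 10, and no failures in ten is compatible with a true rate up to 1 − 0.05^(1/10) = 26% (one-sided 95% limit). It also concerns pain and burns, not stopping.

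**Conclusion.** The point holds as a conflict and an omission on the primary endpoint. Section 4 gives no recurrence contact schedule for a patient who stops after treatments 1 to 4. Sections 3.1 and 3.2.1 do give one, and they disagree with section 4 on when follow-up ends. No section commits to analysing stoppers and switchers in their randomised arm.

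The harm is conditional. It needs section 4 to be followed in practice, stopping to be concentrated in the laser arm, and stoppers to recur clearly more often. In the scenarios shown, the false-positive rate with stoppers lost runs from about 1.5% (equal risk) to 4.9% (12 stoppers at 40%), and it stays below the nominal 2.5% in the milder cases. The change is still worth making before enrolment, because it decides which outcomes are collected and costs very little.

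**What to change.** - **Section 4, Follow-Up:** replace the fifth-visit trigger with monthly contact for every randomised patient to one common one-year endpoint, however many treatments were received. Count the year from a date that every randomised patient has. Align 3.1 and 3.2.1 with it.
- **Sections 7.2.4 and 7.4:** state that stopping or switching treatment is not withdrawal from follow-up. Record the date and reason. The right to stop, switch or withdraw is unchanged.
- **Sections 2.2 and 3.1:** define the two groups by randomised assignment.
- **Section 5.2:** analyse recurrence by that assignment. Add a rule for missing one-year outcomes, with a sensitivity analysis.

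**Cost:** protocol wording and a few extra calls. The laser estimate may be less favourable because stoppers stay in the laser arm. If the planned 5% applies only to patients who complete laser treatment, and stoppers recur at 20%, then 10% stopping gives 0.9 × 5% + 0.1 × 20% = 6.5% in the laser arm and 67.3% power at 82 per arm. With 5% stopping the rate is 5.75% and power is 74.2%. The sponsor should therefore say whether the 5% already allows for stopping.

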5.1. Primary and Secondary Endpoints

Primary endpoints would be the tolerance of the laser depilation treatments based on a pain score consistently <4 and no occurrence of deep second degree burns. These endpoints will be assessed within the first week after each treatment. Secondary endpoints include clinical improvement of pilonidal inflammation and drainage. For Phase Two, the primary endpoint will be the rate of recurrent pilonidal disease at 1 year.

5.2. Statistical Methods

The means/medians and standard deviations/interquartile ranges of the prognostic variables will be evaluated in the total study sample and will be compared between groups (in the phase 2 study) using t-tests or Mann Whitney U tests for continuous variables and chi-squared tests for categorical variables. For the primary outcome of recurrence within one year, we will calculate this proportion and its 95% confidence, based on the exact binomial distribution, in the laser hair depilation group (in the phase 1 study), and we will calculate this proportion and its 95% confidence in both treatment groups (in the phase 2 study) and compare this proportion between groups using a Fisher exact test. SAS version 9.3 (Cary, NC) and Stata version 12 (College Station, TX) will be used in the statistical analyses.

5.3. Sample Size and Power

We anticipate a group of 10 patients to measure laser depilation tolerance. If tolerance is good (>95% the phase 1 patients pain scores < 4 with no deep second degree burns), we will proceed to the phase 2 study. The sample size for phase 2 will be 164 patients. Since the predicted recurrence rate in the control group based on previous studies may be 20% and in the laser group

will be 5%, we would need 82 patients in each treatment group in order to detect this difference at a one-sided alpha of 0.025 using a Fisher exact test.

6. Study Administration

Phase One: Pilot Study

6.1. Data Collection and Management

Patient data such as age, gender, skin type, length of disease, past medical/surgical history, number/date of treatments, treatment parameters, patient pain scores after laser treatments and within the first 12 hours after treatment, and any subsequent episodes of folliculitis/drainage. This information will be kept by the study team and access restricted to the study team.

6.2. Regulatory and Ethical Considerations

6.2.1. Risk Assessment

Patients will be evaluated for their skin type to ensure adequate treatment across the categories.

Laser Depilation Group

Potential risks may include:

- No relief of symptoms
- Recurrence of pilonidal abscess or wound complication
- Photosensitivity or discomfort from laser treatments
- Lastly, loss of confidentiality could be a risk.

No Laser Depilation group

- Loss of confidentiality could be a risk.

6.2.2. Potential Benefits of Trial Participation

Laser Depilation Group

Potential benefits may include:

- Faster relief of symptoms (ex: resolution of pain, erythema)
- Avoiding surgery altogether
 - No risk of surgical complications
- Possible decrease in folliculitis or recurrence

No Laser Depilation Group

- Possible decrease in folliculitis or recurrence due to better hair removal from multiple clinic visits

6.2.3. Risk-Benefit Assessment/Risk Minimization

Laser Depilation Group

Potential benefits include a decrease in the likelihood of recurrent pilonidal disease. The likely risk are pain or burns from laser treatments which will be minimized by applying topical anesthetics and using skin type specific lasers with graded increases in applied power.

6.2.4. Data safety and monitoring

Tolerance to the laser treatments will be monitored closely, especially in the first 48 hours of the laser hair depilation treatments. Treatments will stop at any point in which the patient reports enough discomfort to terminate therapy. Areas treated will be observed for cutaneous changes including excessive erythema, discoloration, or tenderness. Data will be monitored by research team members daily. They will ensure that all data (clinical data and questionnaires) collected are correctly completed. Any suggestion of an adverse event identified by this person will be discussed with the principal investigator immediately.

6.2.5. Adverse events (AE) and Serious adverse events (SAEs)

Any adverse events such as an inability to tolerate the laser therapy or a recurrence will be tracked. Since recurrence is an expected adverse event it will not be reported; however it will be monitored and if we detect an increased rate of recurrence with laser therapy, this will be reported and the trial will be stopped. Mild to moderate pain (pain score 7 or lower) secondary to laser therapy is also consider an expected adverse event and will not be reported. SAEs due to laser treatment include severe pain (pain score 8 or higher) and deep second degree burns.

It is also possible that AE might occur that are not directly related to the study. As such, all AE will be classified as not related (clearly unrelated to study participation), possibly related (temporally related to study participation but could have been caused by other factors), or probably related (temporally related to study participation and cannot be reasonably explained by other factors) to study participation. The clinical study team will review all AE as they occur and determine the seriousness and relatedness of them.

We do not expect any severe AE in either study group. The clinical study team will review any SAE as they occur. All SAE deemed probably related to the study (and all deaths) will be reported to the IRB within 72 hours of discovery.

6.3. Recruitment Strategy

Patients who present to Pediatric Surgery clinic will be approached to evaluate whether they would be interested in taking part in the study. In addition, patients admitted after initial surgical drainage of a pilonidal abscess will be approached to evaluate whether they would be interested in taking part in the study Risks and benefits would be explained, informed consent and assent will be obtained, and we would schedule the patient for their first treatment.

6.4. Informed Consent/Assent

All informed consents and assents will be performed by a physician-member of the research team.

If the child and legal guardian (for subjects < 18 years) are interested in participating in this study, a physician-member of the research team will guide the child and legal guardian through the informed consent/assent process. Written informed consent will be obtained from one legal guardian of subjects < 18 years of age and from the patient him or herself if he or she is ≥ 18 years of age. Written informed assent will be obtained from subjects ≥ 9 and < 18 years of age.

Refusal to participate in the study will not affect the child's clinical care. Participants and their legal guardian have the right to switch to the standard treatment and/or withdraw from the study at any time. Withdrawal from the study will not affect receipt of clinical care.

6.5. Payment to Subjects/Families

Laser depilation treatments will be provided at no cost to the patient. All clinic visits and medications related to the study will be provided at no cost to the patient.

6.6. Confidentiality

Privacy and security will be maintained by minimizing the amount of identifiable data as much as possible. Only study identifications (IDs) will be used to identify patients on all data forms and all datasets used for analysis. The file linking study IDs to patient names and medical record numbers (MRNs) will be password protected and will not be made available to non-study staff or used during data analysis. All study information will be compiled in REDCAP, to which only study staff will have access.

Phase Two: Randomized control trial

7.1. Data Collection and Management

Patient data such as age, gender, skin type, length of disease, past medical/surgical history, number/date of treatments, treatment parameters, patient pain scores after laser treatments and within the first 12 hours after treatment, and any subsequent episodes of folliculitis/drainage. This information will be kept by the study team and access restricted to the study team.

7.2. Regulatory and Ethical Considerations

7.2.1. Risk Assessment

Patients will be evaluated for their skin type to ensure adequate treatment across the categories.

Laser Depilation Group

Potential risks may include:

- No relief of symptoms
- Recurrence of pilonidal abscess or wound complication

- Photosensitivity or discomfort from laser treatments
- Lastly, loss of confidentiality could be a risk.

No Laser Depilation group

- Loss of confidentiality could be a risk.

7.2.2. Potential Benefits of Trial Participation

Laser Depilation Group

Potential benefits may include:

- Faster relief of symptoms (ex: resolution of pain, erythema)
- Avoiding surgery altogether
- No risk of surgical complications
- Possible decrease in folliculitis or recurrence

No Laser Depilation Group

- Possible decrease in folliculitis or recurrence due to better hair removal from multiple clinic visits

7.2.3. Risk-Benefit Assessment/Risk Minimization

Laser Depilation Group

Potential benefits include a decrease in the likelihood of recurrent pilonidal disease. The likely risk are pain or burns from laser treatments which will be minimized by applying topical anesthetics and using skin type specific lasers with graded increases in applied power.

7.2.4. Data safety and monitoring

Tolerance to the laser treatments will be monitored closely, especially in the first 48 hours of the laser hair depilation treatments. Treatments will stop at any point in which the patient reports enough discomfort to terminate therapy. Areas treated will be observed for cutaneous changes including excessive erythema, discoloration, or tenderness. Data will be monitored by research team members daily. They will ensure that all data (clinical data and questionnaires) collected are correctly completed. Any suggestion of an adverse event identified by this person will be discussed with the principal investigator immediately.

